Study Period:	Enrollment Period: Rolling enrollment to the earliest of 2 years or enrollment of 80 subjects Treatment Period: Baseline (Week 0) to Final Evaluation (earlier of 6 months = Week 24 or complete wound closure) Analysis Period: An interim analysis will be conducted when the greater of 20 patients or those enrolled in the two (2) weeks following enrollment of the first participant have completed the Week 12 visit. The full analysis is when all subjects have completed the Final Evaluation.
Phase of Development:	Post-marketing
Objective:	A pressure ulcer (wound/sore) is localized injury to the skin and/or underlying tissue usually over a bony prominence, as a result of pressure, or pressure in combination with shear and/or friction. Primary objective: To compare percentage change in ulcer size in patients with at least one Stage III or Stage IV pressure ulcer in subjects treated with Microcyn versus sterile saline. Secondary objectives: To compare healing progress using the National Pressure Ulcer Advisory Panel’s Pressure Ulcer Scale for Healing (PUSH) score, Version 3.0, and other indicators of wound healing such as time to complete wound closure, elimination of signs of wound infection and to investigate the impact of treatment with Microcyn on subject health care resource utilization (wound-related).
Clinical Hypothesis:	

Name of Sponsor/Company:	Oculus Innovative Sciences, Inc.
Name of Finished Product:	Microcyn [®] Skin and Wound Care with preservatives (“Microcyn”)
Name of Active Ingredient:	N/A
Treatment of pressure ulcers with Microcyn results in faster healing and better overall outcomes than treatment with sterile saline in spinal cord injured adults.	
Design and Methodology:	
Design: Six month (24 week), randomized, open-label, comparative study of treatment of pressure ulcers using Microcyn versus sterile saline.	
Subjects: Adults with spinal cord injuries with at least one Stage III or Stage IV pressure ulcer who meet all eligibility criteria and who have given informed consent.	
Treatment: Microcyn or sterile saline liberally sprayed on wound and permitted to remain on wound which will then be dressed with gauze that is moistened with Microcyn or sterile saline and covered with dry gauze twice daily for the earlier of total wound closure or Week 24.	

Study Visits:

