1.3. STUDY OBJECTIVE

The primary objective is to compare percentage change in wound size in patients with at least one Stage III or Stage IV pressure ulcer in subjects treated with Microcyn versus saline.

The secondary objective is to compare other indicators of wound healing such as time to complete wound closure, elimination of signs of wound infection and to investigate the impact of treatment with Microcyn on subject health care resource utilization (wound-related).

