2.1.2. DURATION

The study duration is up to 6 months (24 weeks) per subject with an enrollment period of up to two years to enroll a total of 80 subjects.

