3.2.5. DISCONTINUATION/WITHDRAWAL PROCEDURES

A subject may voluntarily withdraw from study participation at any time for any reason. If the subject withdraws consent and discontinues from the study, the Investigator will attempt to determine the reason for discontinuation and record the reason in the subject’s records. If a subject withdraws consent because of an AE, that AE should be indicated as the reason for withdrawal. In the event of early discontinuation, (i.e., prior to the earlier of complete wound closure or Week 24) and whenever possible, the subject should be asked to return to the study center to complete the final evaluations. Subjects who withdraw from the study will not be replaced.

If at any time during the study, the Investigator determines that it is not in the best interest of the subject to continue, the subject will be discontinued from participation. The Investigator can discontinue a subject at any time if medically necessary. The Investigator may discontinue a subject’s participation if the subject has failed to follow study procedures or to keep follow-up appointments. Appropriate documentation in the subject’s study record regarding the reason for discontinuation must be completed.

All subjects who fail to return to the study center for follow-up for any visit will be contacted by phone and/or email to determine the reason(s) why the subject failed to return for the necessary visit or elected to discontinue from the study. If a subject is unreachable

by telephone after a minimum of two documented attempts (one attempt on two different days), a registered letter (with duplicate sent by first class mail, postage prepaid) will be sent requesting that contact be made with the Investigator. Only after these attempts have failed will a subject be deemed lost to follow-up.

This study may be terminated in accordance with the Clinical Trial Agreement. Should this be necessary, both Oculus and the Investigator will ensure that proper study discontinuation procedures are completed.

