6. STATISTICAL ANALYSIS

6.1. GENERAL CONSIDERATIONS

All statistical programming will be performed using SAS version 9.1 or higher, or similar statistical program. Statistical significance will be based on two-sided tests at the 5% level of significance. There are two planned analyses. The first will be conducted when the greater of 20 patients or those enrolled in the two (2) weeks following enrollment of the first participant have completed the Week 12 assessments. The second will be when all 80 patients have completed the Week 24 (Final Evaluation) assessments.

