6.3. OVERALL STUDY EVALUATIONS AND MEASUREMENTS

6.3.1. EFFICACY

For the interim analysis, efficacy will be tested via T-tests of percent change in wound size using an intention to treat (ITT) approach as well as a per protocol analysis. For the final analysis, efficacy will be tested via T-tests of percent change in wound size using an intention to treat (ITT) approach as well as a per protocol analysis. Stratification of efficacy results by smoking status and study ulcer Stage will be conducted, although the results are expected to be similar given the stratified randomization.

For the interim analysis and final analyses, secondary analyses will include Kaplan-Meier analysis to estimate time to complete wound closure, and comparisons of infection status of the ulcer. Number and health care resource utilization (wound-related) will be tallied and compared between Microcyn and saline. Other secondary analyses may include linear and logistical regression to estimate the impact of patient characteristics on study endpoints, with special emphasis on variables that affect healing times, such as diabetes. If there are sufficient number of patients with multiple wounds, a mixed effects linear model

will be run, handling the patient as a group that has been randomized to a treatment to determine if there are any spillover effects of treating one wound with Microcyn.

If the interim analysis indicates that the difference in estimated time to complete wound closure between the two populations is 26% or higher at a significance level of $p < 0.05$, the study will be halted early for success.

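### A success stop at the interim halts the whole study with no provision to follow enrolled subjects to Week 24, leaving the six-month wound-size comparison largely unanswered

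*Combined protocol and SAP*

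**What the plan says.** Section 1.3: "The primary objective is to compare percentage change in wound size". Neither the objective nor the endpoint definition in Section 3.5 names a time point. Week 24 is implied by the six-month title, by the Final Evaluation at Week 24 or earlier closure, and by the timing of the final analysis.

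Section 6.1 plans two analyses. The trigger for the first is this: "the greater of 20 patients or those enrolled in the two (2) weeks following enrollment of the first participant have completed the Week 12 assessments". On the other, it says: "The second will be when all 80 patients have completed the Week 24 (Final Evaluation) assessments".

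Section 6.3.1 tests percent change in wound size by t-test at both analyses and attaches no stopping criterion to that test. The stopping criterion is on time to closure, which the synopsis lists as a secondary endpoint: if the "difference in estimated time to complete wound closure between the two populations is 26% or higher" with p < 0.05, "the study will be halted early for success".

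On accrual, Section 2.1.2 gives an "enrollment period of up to two years to enroll a total of 80 subjects", and the synopsis has "Rolling enrollment to the earliest of 2 years or enrollment of 80 subjects".

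On termination, Section 3.2.5 refers to the Clinical Trial Agreement and says that "both Oculus and the Investigator will ensure that proper study discontinuation procedures are completed". The same section asks subjects who discontinue early to return for final evaluations where possible.

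**The concern.** The point is the data lost by halting. It is separate from the error rate of the rule, since even a well-calibrated rule would lose them.

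The object of the halt is the study, not enrolment. Read literally, subjects already randomised and under treatment would leave before Week 24, and the second analysis could not take place as Section 6.1 defines it. No primary analysis is defined for a stopped study. The trial could then be declared a success on a secondary endpoint, with its wound-size comparison available mainly at Week 12.

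The loss would also be selective. A subject whose ulcer closes early has a Final Evaluation at closure, whereas one whose ulcer is still open at the halt would have no Week 24 size. Whether a final outcome exists would then depend on the outcome itself.

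**Working it through.** The plan has no figure to reproduce: the sample of 80 is described as a convenience sample without power inputs, and no count of subjects expected at Week 24 at the interim is given. The check is accrual arithmetic.

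**Inputs from the documents.** Planned size 80 and an accrual window of up to 2 years, taken as 104 weeks (Section 2.1.2, synopsis); interim at 20 patients through Week 12 (Section 6.1); 24 weeks per subject; two-sided 5% (Section 6.1).

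**Assumptions.** Uniform accrual at r subjects per week, and no dropout among the first 20.

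**Formulas.**
- Entry of the 20th subject: 20/r. Interim: 20/r + 12 weeks.
- Enrolled at the interim: r × (20/r + 12) = 20 + 12r, capped at the number accrued.
- At Week 24 at the interim: those enrolled at least 12 weeks before the 20th, so max(0, 20 − 12r).

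**Worked case, 80 over 104 weeks.** r = 80/104 = 0.769. The 20th subject enters at week 26 and the interim falls at week 38. Enrolled: 20 + 12 × 0.769 = 29.2. At Week 24: 20 − 9.2 = 10.8.

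| Accrual | r per week | Interim (week) | Enrolled | At Week 24 |
|---|---|---|---|---|
| 80 in 104 weeks | 0.769 | 38.0 | 29.2 | 10.8 |
| 80 in 78 weeks | 1.026 | 31.5 | 32.3 | 7.7 |
| 80 in 52 weeks | 1.538 | 25.0 | 38.5 | 1.5 |
| 80 in 48 weeks | 1.667 | 24.0 | 40.0 | 0 |
| 60 in 104 weeks | 0.577 | 46.7 | 26.9 | 13.1 |
| 40 in 104 weeks | 0.385 | 64.0 | 24.6 | 15.4 |
| 20 in 104 weeks | 0.192 | 116.0 | 20 | 17.7 |

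The last three rows are allowed because the synopsis lets enrolment close at two years short of 80.

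**Sensitivity.**
- Counting subjects discretely in the first row gives 10 to 11 at Week 24.
- Ramped accrual, N(t) = 80(t/104)^k with k = 1.5, 2, 3 and 5, gives 11.9, 11.8, 10.9 and 8.8.
- If more than 20 enrol in the first two weeks, the interim falls at about week 14 and none has reached Week 24.
- Ceiling: when 20 patients trigger the interim, the last of them is only at Week 12, so at most 19 can be at Week 24. That is under a quarter of 80 (19/80 = 24%).

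**Precision of a 24-week comparison.** Two-sample t-test, two-sided 5%, 80% power, noncentral t, no dropout:
- 11 subjects (5.5 per arm): 1.90 SD detectable.
- 29 subjects (14.5 per arm): 1.08 SD.
- 40 subjects (20 per arm): 0.91 SD.

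Faster accrual widens the gap: more subjects are enrolled at the interim and fewer have finished.

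**The case against.** **The primary endpoint is tested at the interim.** This stands. A reader might infer that a success stop would have no primary-endpoint result behind it, and the documents do not support that. Section 6.3.1 t-tests percent change at the interim, and Section 6.2 admits to the efficacy population anyone with a baseline and at least one follow-up visit. What would be missing is most of the 24-week result.

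**Week 24 is not stated as the primary time point.** Also correct. It is inferred from the design, and the point should be read with that qualification.

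**None to about 11 is not a limit.** Correct. A reader might take it as the full range the plan allows, but it assumes that 80 accrue evenly in 48 to 104 weeks. Slower accrual gives about 13 to 18, and the ceiling is 19. This changes the number but not the direction.

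**Early closers already have final outcomes.** True, and the rule needs closures in order to be met, so the 11-subject precision figure leaves out some usable outcomes. But these come only from healed ulcers, so they add to the selectivity described above.

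**Section 3.2.5 asks discontinued subjects back for final evaluations, and the Clinical Trial Agreement may say more.** The request applies only where possible, and at a halt most such visits would fall before Week 24. The agreement is not among the documents, so the silence is established only for the protocol.

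**Halting may have been meant to stop enrolment only.** That is possible, since the term is not defined. In that case the fix records the intent, and it is better settled before interim results are known.

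**Conclusion.** The point holds as a cheap improvement. Followed literally, Section 6.3.1 ends the study on a secondary endpoint while most enrolled subjects are short of Week 24, and the only remaining analysis in Section 6.1 can then no longer occur. The six-month wound-size comparison would be largely unanswered, though percent change would have been tested on mainly Week 12 data.

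Under even accrual of 80 in 48 to 104 weeks, 0 to about 11 of roughly 40 to 29 enrolled subjects would have reached Week 24. If accrual closes at two years with 20 to 60 subjects, the figure is about 13 to 18. These counts rest on assumed accrual rates, because the plan gives none. The conclusion does not depend on the exact rate, since even the ceiling of 19 is under a quarter of the planned sample. The consequence arises only if the stopping rule is met.

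**What to change.** Two passages need to change together.

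- **Section 6.3.1**, replace the halt with: *If the rule is met, enrolment stops. All enrolled subjects are asked to complete their scheduled assessments through Week 24. The primary percent-change analysis is then run on all randomised subjects and reported with the closure result.*
- **Section 6.1**, replace the trigger of the second analysis with: *The final analysis takes place when all enrolled subjects (80, or those enrolled at an early stop) have completed the Final Evaluation.*

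The wording covers assessments only. What treatment subjects receive after a stop is a clinical matter that it leaves open.

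Cost: two short edits, plus at most about 24 further weeks of visits that are already scheduled, so the full report comes later than under an outright halt. Precision stays limited. With 29 subjects and no dropout, about 1.1 SD is detectable, against about 1.9 SD with 11, so the change preserves the six-month data without making that comparison well powered.

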6.3.2. SAFETY

Adverse event analyses will be conducted for the interim and final analyses. Safety analyses will be conducted via Fischer's exact tests, chi-square, and t-tests, as applicable. The safety population will include all subjects exposed to the study product who have provided any post-treatment safety information.

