The sample is a convenience sample of 80 patients.	

LIST OF ABBREVIATIONS AND DEFINITIONS OF TERMS

Abbreviation	Definition
AE	Adverse Event
ASIA	American Spinal Cord Injury Association
CFR	Code of Federal Regulations
CTEP-	Cancer Therapy Evaluation Program – Common Terminology Criteria for
FDA	Food and Drug Administration
GCP	Good Clinical Practices
HHS	Health and Human Services
ICH	International Conference on Harmonisation
IEC	Independent Ethics Committee
IRB	Institutional Review Board
ITT	Intention To Treat
MedDRA	Medical Dictionary for Regulatory Activities
NPUAP	National Pressure Ulcer Advisory Panel
PUSH	Pressure Ulcer Scale for Healing
SAE	Serious Adverse Event
SAS	Statistical Analysis Software
SOP	Standard Operating Procedure
UPT	Urine Pregnancy Test
US	United States
WOCBP	Woman of Childbearing Potential

COVER PAGE ERROR! BOOKMARK NOT DEFINED.

SIGNATURE PAGE 2

INVESTIGATOR'S AGREEMENT 3

PROTOCOL SYNOPSIS..... 4

LIST OF ABBREVIATIONS AND DEFINITIONS OF TERMS..... 9

1. INTRODUCTION AND BACKGROUND..... 12

 1.1. STUDY RATIONALE 15

 1.2. DOSE RATIONALE 16

 1.3. STUDY OBJECTIVE..... 16

 1.4. CLINICAL HYPOTHESES..... 16

2. STUDY DESIGN..... 17

 2.1. OVERALL DESIGN..... 17

 2.1.1. *Structure*..... 17

 2.1.2. *Duration* 17

 2.1.3. *Controls*..... 17

 2.1.4. *Dosage/Dose Regimen*..... 17

 2.2. TEST ARTICLE 17

 2.3. STUDY POPULATION 17

 2.4. ELIGIBILITY CRITERIA..... 17

 2.4.1. *Informed Consent and Authorization to Release Health Information*..... 17

 2.4.2. *Inclusion Criteria*..... 19

 2.4.3. *Exclusion Criteria*..... 19

3. STUDY PROCEDURES AND METHODS..... 21

 3.1. SUBJECT ENTRY PROCEDURES..... 21

 3.2. SCHEDULE OF VISITS AND PROCEDURES 21

 Table 1: Schedule of Visits and Procedures 21

 3.2.1. *Baseline Visit* 21

 3.2.2. *follow-up visits (Weeks 4, 8, 12, 16, 20)*..... 24

 3.2.3. *subject application instructions*..... 26

 3.2.4. *subject restrictions* 26

 3.2.5. *Discontinuation/Withdrawal Procedures*..... 26

 3.3. VARIATION FROM SCHEDULED VISIT DAYS..... 27

 3.4. SAFETY ASSESSMENTS 27

 3.4.1. *adverse events*..... 27

 3.5. EFFICACY ASSESSMENTS..... 27

 3.5.1. *Time to wound closure*..... 27

 3.6. SCREEN FAILURES..... 27

 3.7. PROTOCOL DEVIATIONS..... 28

4. PROHIBITED MEDICATIONS AND TREATMENTS..... 29

Table 2: Prohibited Medications and Treatments	29
5. EVALUATION OF ADVERSE EVENTS.....	30
5.1. DEFINITIONS.....	30
5.1.1. Adverse Event Severity Grades	32
5.1.2. Study product Causality	33

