3.2.1. BASELINE VISIT

The following procedures must be performed and recorded at the Baseline (Week 0) visit, gathered from the patient in the clinic unless otherwise specified:

1. Review study procedures and information regarding the study with the subject and obtain written informed consent
2. Review eligibility criteria; inclusion/exclusion (see Section 2.4.2 and Section 2.4.3)
3. For women of childbearing potential, obtain screening urine pregnancy test
4. Obtain demographic information and relevant medical/social history (from chart)
 - a. *Demographics*: age, race (Caucasian, African-American, Hispanic, mixed race, other), gender, marital status, employment status, education (\leq high school, some college, \geq college), insurance status (Medicare, Medicaid, private insurance, other, no insurance) including identification of whether plan is managed care or fee-for-service.
 - b. *Medical/social*
 1. Height (feet/inches), weight (lbs)
 2. Smoking status (current, former, never)
 3. Alcohol (drink every day, a few drinks per week, a few drinks per month, seldom drink, abstain)
 4. Diabetes (yes, no) (from chart)
 5. Injury information (from chart)
 - a) Date of injury
 - b) Injury level (C1-8, T1-12, L1-5)
 - c) American Spinal Cord Injury Impairment Scale (ASIA) score (if known)
 - a. ASIA A – complete, no motor or sensory function is preserved in sacral segments S4-S4
 - b. ASIA B – incomplete, sensory but not motor function is preserved below the neurological level and includes the sacral segments S4-S5.
 - c. ASIA C – incomplete, motor function is preserved below the neurological level, and more than half of key muscles below the neurological level have a muscle grade less than 3.

- d. ASIA D - Incomplete: Motor function is preserved below the neurological level, and at least half of key muscles below the neurological level have a muscle grade of 3 or more.
 - e. ASIA E = Normal: motor and sensory functions are normal.
 - 6. Current antibiotic use
 - 7. Results of any potentially relevant clinical laboratory tests, e.g., albumin, hemoglobin, performed at or within 14 days of baseline.
- 5. Patients will be stratified according to (1) smoking status; and (2) study ulcer Stage. Following stratification, patients will be randomized to study product (Microcyn or sterile saline). Document study pressure ulcer.

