5.1. DEFINITIONS

An adverse event is an unfavorable change in health, including abnormal laboratory findings, that occurs in trial participants during the clinical trial or within a specified period following the trial. For purposes of this Protocol, the specified period is Weeks 0-24 (per patient).

An MDR reportable event is one that reasonably suggests that a marketed device has or may have caused or contributed to a death, serious injury, or has malfunctioned, and that the device or a similar device marketed by the manufacturer would be likely to cause or contribute to a death or serious injury if the malfunction were to recur. Serious Adverse Events include adverse events that result in death, require either inpatient hospitalization or the prolongation of hospitalization, are life-threatening, result in a persistent or significant disability/incapacity or result in a congenital anomaly/birth defect. Other important medical events, based upon appropriate medical judgment, may also be considered Serious Adverse Events if a trial participant's health is at risk and intervention is required to prevent an outcome mentioned.

Serious injury/(serious illness) is an injury or illness that:

- is life threatening, even if temporary in nature;
- results in permanent impairment of a body function or permanent damage to a body structure; or
- necessitates medical or surgical intervention to preclude permanent impairment of a body function or permanent damage to a body structure.

A complaint is any written, electronic or oral communication that alleges deficiencies related to the identity, quality, durability, reliability, safety, effectiveness, or performance of a device after it is released for distribution.

A malfunction is a failure of the device to meet its performance specifications or otherwise perform as intended. Performance specifications include all claims made in the labeling for the device. A reportable malfunction is a malfunction for which:

- the chance of a death or serious injury resulting from a recurrence of the malfunction is **not** remote;
- the consequences of the malfunction affect the device in a catastrophic manner that may lead to a death or serious injury;
- the malfunction causes the device to fail to perform its essential function and compromises the device's therapeutic, monitoring or diagnostic effectiveness which could cause or contribute to a death or serious injury, or other significant adverse device experiences; or

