6.2. POPULATIONS

All subjects will be included in the summaries of demographic and other baseline characteristics. The safety population will include all subjects ever exposed to any study product (Microcyn and saline) and have provided any post-treatment safety information. The Efficacy population will include all subjects who complete both a Baseline (Week 0) and at least one follow up visit.

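### The planned between-arm safety comparison is hypothesis tests only, with no estimate or interval, in a sample too small for those tests to be informative

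*Combined protocol and SAP*

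**What the plan says.** The synopsis (Efficacy Evaluations) lists adverse events among the secondary endpoints. Section 6.3.2 gives the comparison: "Safety analyses will be conducted via Fischer's exact tests, chi-square, and t-tests, as applicable". The synopsis names the same three tests. Section 6.3.2 applies the analysis at both looks: "Adverse event analyses will be conducted for the interim and final analyses". The decision level is the general one in Section 6.1: "Statistical significance will be based on two-sided tests at the 5% level of significance". It is not written for safety in particular.

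The sample size was not derived from any safety or efficacy target. The synopsis says: "The sample is a convenience sample of 80 patients". Section 3.2.5 adds: "Subjects who withdraw from the study will not be replaced". The safety population (Section 6.2) is exposed subjects with some post-treatment safety information, so it is at most 80.

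The documents give no allocation ratio, no expected adverse event rate in either arm, no counting unit (subjects or events), no by-arm adverse event summary and no interval for a safety difference.

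**The concern.** With about 40 subjects per arm, a safety p-value mostly reflects sample size. A result above 0.05 can arise with no excess of harm or with a large one, and the p-value does not tell them apart. An estimate with an interval shows how much excess the data still allow, and that is what a reader of the safety section needs. If 6.3.2 is followed as written, no such quantity is planned at either analysis. The interim look, triggered by at least 20 patients, is weaker still.

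**Working it through.** **Inputs.** Two-sided level 0.05 (Section 6.1). Total 80 (synopsis). Equal arms of 40 are an assumption. All event rates below are illustrative assumptions. The unit is subjects with at least one event, also an assumption. There is no stated power or detectable safety difference to reproduce.

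**1. Fisher's exact test, 5/40 versus 0/40.** With five subjects with events among 80, the probability that all five fall in one named arm is C(40,5)/C(80,5) = 658,008/24,040,016 = 0.0274. The opposite table is equally likely, so the two-sided p = 2 × 0.0274 = 0.055. One more subject, 6 versus 0, gives p = 0.026.

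**2. Risk difference and interval for the same table.** Difference = 5/40 − 0/40 = 12.5 points. The Newcombe interval combines the Wilson 95% limits of each arm: 5.46% to 26.11% for 5/40, and 0% to 8.76% for 0/40.
- Lower: 0.125 − √[(0.125 − 0.0546)² + (0.0876 − 0)²] = 0.125 − 0.112 = 0.013
- Upper: 0.125 + √[(0.2611 − 0.125)² + (0 − 0)²] = 0.261

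The 95% interval is therefore 1.3 to 26.1 points. It excludes zero although Fisher p exceeds 0.05. The two methods are not inversions of each other, and Fisher's test is conservative at small counts.

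**3. Other results that miss 5% by Fisher's test at 40 per arm.**

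| Subjects with event | Fisher p | Difference (points) | Newcombe upper limit (points) |
|---|---|---|---|
| 7 vs 1 | 0.057 | 15.0 | 29.6 |
| 8 vs 2 | 0.087 | 15.0 | 30.2 |
| 11 vs 4 | 0.083 | 17.5 | 34.0 |

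**4. Power of Fisher's test.** Power = Σ Bin(a; 40, p₁) × Bin(b; 40, p₂) over all tables (a, b) with p < 0.05:
- 20% versus 5%: 41%
- 15% versus 2%: 36%
- 20% versus 10%: 16%

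**5. Interim.** At 10 per arm (20 patients, 1:1 assumed), 4 versus 0 gives Fisher p = 0.087. Power for 20% versus 5% is 2%.

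**6. Sensitivity to the split.** With 39/41 and all five events in the smaller arm, the observed table has probability C(39,5)/C(80,5) = 575,757/24,040,016 = 0.024. The opposite table has probability C(41,5)/C(80,5) = 749,398/24,040,016 = 0.031. That is more likely than the observed table and is not counted, so p = 0.024. With the events in the larger arm (5/41 versus 0/39), both tables count and p = 0.024 + 0.031 = 0.055. Equal arms of 32 to 36, allowing for dropout, give p = 0.053 to 0.054.

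**7. Chi-square on the same tables.** χ² = N(ad − bc)²/(product of the four margins).
- 5 versus 0: 80 × 200²/(40 × 40 × 5 × 75) = 5.33, p = 0.021. With Yates correction, 80 × 160²/600,000 = 3.41, p = 0.065.
- 11 versus 4: 80 × 280²/(40 × 40 × 15 × 65) = 4.02, p = 0.045, against Fisher 0.083.

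**The case against.** **No conclusion rule exists.** A reader might infer that the trial will declare no safety difference whenever p is 0.05 or more. The documents contain no safety hypothesis, no safety success criterion and no such statement. This objection stands: the misreading is a risk of test-only output, not something the plan prescribes.

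**Safety is not handled by p-values alone.** Events are recorded at each visit, graded for severity (Section 5.1.1), documented so that the sponsor can submit registry summaries, and, where product-related and serious, reported within 24 hours (Section 5.3). None of this waits on a test. This also stands, so the point is confined to the between-arm comparison. Case-level review does not compare arms, and registry summaries are not a pre-specified between-arm estimate.

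**The choice of test.** It is tempting to say that the plan names two tests that give opposite verdicts. At 5 versus 0 the expected count is 2.5 per arm. The sentence in 6.3.2 leaves the choice to applicability, which would ordinarily lead to Fisher's test, and Yates-corrected chi-square agrees with Fisher there. A small gap remains: at 11 versus 4 the expected count is 7.5 per arm, the usual small-count convention does not settle the matter, and uncorrected chi-square and Fisher fall on opposite sides of 5%. Naming one test closes it.

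**The example is fragile and the rates are invented.** Both are true. The 5 versus 0 verdict changes with a 39/41 split, and total event counts over 24 weeks may not be small. The low power at 40 per arm does not rest on that one table.

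**Any trial this size has low power for adverse events, and an interval can be added at reporting.** Also true. That is a reason to plan estimation from the start, since intervals added later are at the discretion of whoever writes the report.

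**Conclusion.** The concern holds as a gap in the planned safety analysis: tests only, no estimate or interval, in a sample not sized for the purpose. Under assumed equal arms of 40 and illustrative rates, Fisher's test would miss a true 20% versus 5% difference about 59% of the time (100 − 41) and a 20% versus 10% difference about 84% of the time (100 − 16). A non-significant 5/40 versus 0/40 leaves room for an excess of about 26 points. The exact p-value for that table depends on the split: 0.055 at 40/40, and 0.024 at 39/41 with the events in the smaller arm.

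The documents do not support going further and saying that the trial will report no difference, or that all safety judgement rests on significance. The change is a worthwhile, cheap improvement. It does not affect whether the trial can run.

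**What to change.** In Section 6.3.2 and the matching synopsis text:

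1. For any adverse event, any serious adverse event and any adverse event at the study ulcer, report the number and percentage of subjects per arm and the risk difference with a 95% confidence interval (Newcombe, for example), at the interim and final analyses. Make this the main safety summary, with the subject as the counting unit.
2. Keep Fisher's exact test as the only test for proportions, labelled supportive. Note that a Newcombe interval can exclude zero when Fisher p is above 0.05, as at 5 versus 0, so that the two are not presented as contradictory.
3. State that a non-significant result is not evidence of no safety difference.

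The cost is a few sentences and table columns, with no extra visits or subjects. The fields of the adverse event form are not shown in the documents, so check that it lets an event be attributed to the study ulcer. The one real downside for the sponsor is a safety statement that reads as less reassuring, because the intervals will be wide.
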